5.1.5 Planned Study Calendar

The following dates are approximate. The actual dates may differ as, for example, the study will not start until all the appropriate regulatory and ethical approvals have been obtained.

Planned study periods/dates:

(FVFS [first visit, first subject] to LCLS [last contact, last subject]: Q3 2019 ~ Q2 2021

Inclusion period (FVFS to FVLS [first visit, last subject]: Q3 2019 ~ Q3 2020

Vaccination period: Q3 2019 ~ Q3 2020

Date of final clinical study report: Q3 2021

5.2 Enrollment and Retention of Study Population

5.2.1 Recruitment Procedures

Before the start of the trial, the Investigator or delegate will contact an appropriate pool of potential subjects and invite them to participate in the study. The site will ensure that any advertisements used to recruit subjects (letters, pamphlets, posters) are submitted to the Sponsor prior to submission to the IEC / IRB for approval.

Recruitment procedures and materials will be submitted for IEC / IRB approval or favorable opinion before implementation.

5.2.2 Informed Consent Procedures

Informed consent is the process by which a subject voluntarily confirms his or her willingness to participate in a particular study. Informed consent must be obtained before any study procedures are performed. The process is documented by means of a written, signed, and dated ICF.

In accordance with GCP, prior to signing and dating the consent form, the subject must be informed by appropriate study personnel about all aspects of the study that are relevant to making the decision to participate, and must have sufficient time and opportunity to ask any questions.

The actual ICF used at each center may differ, depending on local regulations and IEC / IRB requirements. However, all versions must contain the standard information found in the sample ICF provided by the Sponsor. Any change to the content of the ICF must be approved by the Sponsor and the IEC / IRB prior to the form being used.

If new information becomes available that may be relevant to the subject's willingness to continue participation in the study, this will be communicated to him / her in a timely manner. Such information will be provided via a revised ICF or an addendum to the original ICF.

ICFs will be provided in duplicate, or a photocopy of the signed consent will be made. The original will be kept by the Investigator, and the copy will be kept by the subject

Documentation of the consent process should be recorded in the source documents.

5.2.3 Screening Criteria

There are no screening criteria other than the inclusion and exclusion criteria.

5.2.4 Inclusion Criteria

An individual must fulfill *all* of the following criteria to be eligible for study enrollment:

- 1) Aged ≥ 18 years on the day of inclusion^a
- 2) ICF has been signed and dated by the subject
- 3) Able to attend all scheduled visits and to comply with all trial procedures
- 4) Body Mass Index (BMI): $18.5 \text{ Kg/m}^2 \leq \text{BMI} \leq 30 \text{ Kg/m}^2$
- 5) Covered by health insurance

5.2.5 Exclusion Criteria

An individual fulfilling *any* of the following criteria is to be excluded from study enrollment:

- 1) Subject is pregnant, or lactating, or of childbearing potential and not using an effective method of contraception or abstinence from at least 4 weeks prior to the first vaccination until at least 4 weeks after the last vaccination. To be considered of non-childbearing potential, a female must be post-menopausal for at least 1 year, or surgically sterile.

^a " ≥ 18 years" means from the day of the 18th birthday onwards, with no upper age limit."

- 2) Participation at the time of study enrollment or, planned participation during the present trial period in another clinical trial investigating a vaccine, drug, medical device, or medical procedure.
- 3) Subject who would receive more than 4 500 euros as indemnities for his/her participation in biomedical research within the 12 last months, including the indemnities for the present study.
- 4) Subject in the exclusion period of a previous study or subject who refuses to be on the national registry of subjects that participate in biomedical research (ie," Fichier National des Volontaires pour la Recherche Biomédicale VRB")
- 5) Receipt of any vaccine in the 4 weeks (28 days) preceding the first trial vaccination or planned receipt of any vaccine prior to Visit 7.
- 6) Previous vaccination against rabies (in pre- or post-exposure regimen) with either the trial vaccines or another vaccine
- 7) Receipt of immune globulins, blood or blood-derived products in the past 3 months
- 8) Known or suspected congenital or acquired immunodeficiency; or receipt of immunosuppressive therapy, such as anti-cancer chemotherapy or radiation therapy, within the preceding 6 months; or long-term systemic corticosteroid therapy (prednisone or equivalent for more than 2 consecutive weeks within the past 3 months)
- 9) At high risk for rabies exposure during the trial^a
- 10) Known systemic hypersensitivity to any of the vaccine or HRIG components, or history of a life-threatening reaction to the vaccines used in the trial or to a vaccine containing any of the same substances^b
- 11) Self-reported thrombocytopenia, contraindicating IM vaccination
- 12) Bleeding disorder, or receipt of anticoagulants in the 3 weeks preceding inclusion, contraindicating intramuscular vaccination
- 13) Deprived of freedom by an administrative or court order, or in an emergency setting, or hospitalized involuntarily
- 14) Current alcohol or substance abuse that, in the opinion of the Investigator, might interfere with the trial conduct of completion.

^a Such as veterinarians and their staff, animal handlers, rabies researchers, and certain laboratory workers, persons whose activities bring them into frequent contact with rabies virus or potentially rabid bats, raccoons, skunks, cats, dogs, or other species at risk for having rabies, people travelling where rabies is enzootic.

^b The components of VRVg-2 are listed under Investigational Product and in the Investigator's Brochure Section 3.2. The components of Verorab and Imovax Rabies vaccines are listed under Control Products, and the components of HRIG, under Other Product. (See [Section 6.1](#) to [Section 6.4](#))

- 15) Chronic illness that, in the opinion of the Investigator, is at a stage where it might interfere with trial conduct or completion^a
- 16) Moderate or severe acute illness/infection (according to Investigator judgment) on the day of vaccination or febrile illness (temperature $\geq 38.0^{\circ}\text{C}$). A prospective subject should not be included in the study until the condition has resolved or the febrile event has subsided
- 17) Personal history of Guillain-Barré syndrome
- 18) Identified as an Investigator or employee of the Investigator or study center with direct involvement in the proposed study, or identified as an immediate family member (ie, parent, spouse, natural or adopted child) of the Investigator or employee with direct involvement in the proposed study

If the subject has a primary physician who is not the Investigator, the site may contact this physician with the subject's consent, to inform him / her of the subject's participation in the study.

5.2.6 Medical History

Prior to enrollment, subjects will be assessed for pre-existing conditions and illnesses, both past and ongoing. Any such conditions will be documented in the source document. Significant (clinically relevant) medical history (reported as diagnosis) including conditions/illnesses for which the subject is or has been followed by a physician or conditions/illnesses that could resume during the course of the study or lead to an SAE or to a repetitive outpatient care will be collected in the case report book (CRB). The significant medical history section of the CRB contains a core list of body systems and disorders that could be used to prompt comprehensive reporting, as well as space for the reporting of specific conditions and illnesses.

For each condition, the data collected will be at least:

- Diagnosis (this is preferable to reporting signs and symptoms)
- Presence or absence of the condition at enrollment

The reporting of signs and symptoms in lieu of a diagnosis is strongly discouraged.

Dates, medications, and body systems are not to be recorded, and the information collected will not be coded. Its purpose is to assist in the later interpretation of safety data collected during the study. Given the current COVID-19 pandemic, the medical history must actively include if suspected/confirmed COVID-19 happened, dates, treatments received and dosages. The use of medications (prescribed or out-of-the-counter) such as chloroquine and hydroxychloroquine within at least 2 months before enrollment should be recorded, given their interference with rabies vaccines (22) (27).

^a Chronic illness may include, but is not limited to, neurological, cardiopulmonary, gastrointestinal, renal, genitourinary, metabolic, hematologic, auto-immune, or psychiatric disorders or infection.

5.2.7 Contraindications for Subsequent Vaccinations

5.2.7.1 Temporary Contraindications

Should a subject experience one of the conditions listed below, the Investigator will postpone further vaccination until the condition is resolved or until the clinical hold is lifted. Postponement must still be within the timeframe for vaccination indicated in the Table of Study Procedures. If any dose is delayed, the subsequent doses should be delayed according to the original time interval.

- 1) Moderate or severe acute illness/infection (according to Investigator's judgment) on the day of vaccination or febrile illness (temperature $\geq 38.0^{\circ}\text{C}$)
- 2) Clinical hold as instructed by the Sponsor, ANSM, or other regulatory authority

5.2.7.2 Definitive Contraindications

Should a subject experience 1 of the conditions listed below, the Investigator will discontinue vaccination:

- Pregnancy, as indicated by a positive urine test
- Anaphylactic or other significant allergic reaction to the previous dose of vaccine
- Immunoglobulin, blood or blood-derived products received in the past 3 months or ongoing at the visit
- Immunosuppressive therapy such as anti-cancer chemotherapy or radiation therapy in the past 6 months or ongoing at the visit, or long-term systemic corticosteroid therapy (for more than 2 consecutive weeks in the past 3 months before the visit)
- HIV seropositivity
- Thrombocytopenia, bleeding disorder or receipt of anticoagulants contraindicating IM vaccination
- Administration of a vaccine other than the study vaccine between D0 and V07 (VAC5+28D)
- An SAE related to the trial vaccines following a vaccination.
- Any potential contact with rabies virus during the course of the study.
- Reporting of Guillain-Barré syndrome

Subjects with a definitive contraindication will continue to be followed up for the study-defined safety and possibly immunogenicity assessments, as applicable.

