--	---

Table of Study Procedures

Phase III Trial, 7 Visits, 1 Phone call, 5 Vaccinations, 4 Blood Samples, 7 Months Period per Subject

Visit	V01	V02	V03	V04	V05	V06	V07	Phone Call
Visit interval	VAC1	VAC2= VAC1+3D	VAC3= VAC1+7D	VAC4= VAC1+14D	VAC5= VAC1+28D	VAC5+14D	VAC5+28D	VAC5*+6M
Indicative days (D)/Months (M)	D0	D3	D7 +1D	D14 ±1D	D28 ±3D	D42 ±3D	D56 ±3D	M7 +14D
Informed consent signed	√							
Demographic data	√							
Urine pregnancy test†	√	√	√	√	√			
Physical examination‡	√	√	√	√	√	√	√	
Past and current significant medical history	√							
Inclusion & exclusion criteria	√							
Randomization	√							
Blood sampling for serology (6 mL)	√			√	√	√		
Vaccine injection	√	√	√	√	√			
HRIG administration§	√							
30-minute observation period	√	√	√	√	√			
Diary card (DC) Memory aid (MA) Provided Checked Collected	DC1	DC1	DC1	DC2 DC1 DC1	DC3 DC2 DC2	DC3	MA DC3 DC3	MA
Injection site reactions and systemic event assessment	√	√	√	√	√	√	√	
Temporary contraindications		√	√	√	√			
Definitive contraindications		√	√	√	√			
Reportable concomitant medication	√	√	√	√	√	√	√	
Termination record							√	
Pregnancy cases	Collected throughout the entire study period							
SAEs and AESIs	Collected throughout the entire study period							

*VAC5 or last vaccine injection in the event of early terminated subject, contacted for the 6 months follow-up period through a phone call

†For female subjects of childbearing potential

‡Complete physical examination at V01 and medically-driven physical examination for remaining visits

§With the exception of subjects from Group 4 (who will receive VRVg-2 only)

Abbreviations: AESI: adverse event of special interest; D: day; DC: diary card; HRIG: human rabies immunoglobulin; MA: memory aid; SAE: serious adverse event; V: visit; VAC: vaccination.

List of Abbreviations

ACIP	Advisory Committee on Immunization Practice
AE	adverse event
AESI	adverse event of special interest
Ag	antigen
ANSM	Agence Nationale de Sécurité du Médicament et des Produits de Santé
AR	adverse reaction
BMI	body mass index
CDM	Clinical Data Management
CI	confidence interval
CPRV	chromatographically purified rabies vaccine
CQA	Clinical Quality Assessment
CRA	Clinical Research Associate
CRB	(electronic) case report book [all the case report forms for a subject]
CRF	(electronic) case report form
CRO	Contract Research Organization
CTA	clinical trial agreement
CTL	Clinical Team Leader
COVID-19	Coronavirus Disease 2019
DC	diary card
DNA	deoxyribonucleic acid

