5.1 Description of the Overall Study Design and Plan

5.1.1 Study Design

This will be a multi-center, modified double-blind (Groups 1 to 3)/open (Group 4), controlled, randomized, Phase III study in 636 subjects aged ≥ 18 years. Subjects will receive 5 vaccine injections of either VRVg-2 (Groups 1 and 4), Verorab vaccine (Group 2), or Imovax Rabies vaccine (Group 3), at day [D] 0, D3, D7, D14, and D28 (ESSEN regimen). All groups with the exception of Group 4 will additionally receive HRIG at D0.

Vaccination and HRIG will be administered through the IM route.

Subjects will be randomized 3:1:1:1 (Group 1, 2, 3, and 4, respectively) with the resulting number of subjects assigned to each study group shown in [Table 5.1](#).

Table 5.1: Distribution of subjects according to vaccination group

	Vaccine	Number of subjects*
Group 1	VRVg-2 + HRIG	318
Group 2	Verorab® + HRIG	106
Group 3	Imovax® Rabies + HRIG	106
Group 4	VRVg-2	106

*Justification of the sample size is given in [Section 12.5](#).

All subjects will provide blood samples before the first vaccination at D0 (baseline titer) and for the assessment of the immune response to the rabies vaccines at D14 (7 days after the third vaccine injection), D28 (14 days after the fourth vaccine injection), and D42 (14 days after the last vaccine injection).

[figure not shown]
Safety will be assessed in all subjects during the vaccination period and up to 28 days after vaccinations, in terms of occurrence of AEs, SAEs and adverse events of special interest (AESIs). In addition, SAEs and AESIs will be collected up to 6 months after the last vaccination in all subjects.

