- 13) Keep the subject under observation for 30 minutes, and record any AR in the source document.

^a In case of any safety finding after the start of the study, ANSM can request to provide an addendum to the ICF. This ICF addendum should be signed additionally at any other visit before further procedures.

- 14) Give the subject the first diary card (DC1), a thermometer, and a ruler, and go over the instructions for their use.
- 15) Remind the subject to bring back DC1 when they return for V02 at a specified date and time.
- 16) Remind the subject to notify the site in case of a SAE and AESI.
- 17) For woman of childbearing potential: remind the subject to notify the site in case of pregnancy.
- 18) Complete the relevant source document information and CRF pages for this visit.

V02 (3 days after VAC1): Collection of Safety Information and Vaccination

- 1) Review the DC1 with the subject, including any AEs, SAEs, AESIs, medications, or therapy that occurred since vaccination by Investigator or delegate. The subject will continue using the DC1 to collect safety information until the V04.
- 2) Urine pregnancy test, if applicable.
- 3) Conduct a physical examination, including temperature.
- 4) Check contraindication for subsequent vaccinations (see [Section 5.2.7](#)).
- 5) Contact the IRT system for dose number assignment (see [Section 6.6](#)).
- 6) Inject the appropriate study vaccine (VAC2) in the opposite arm as compared to the VAC1.
- 7) Keep the subject under observation for 30 minutes, and record any AR in the source document.
- 8) Remind the subject to bring back DC1 when they return for V03 at a specified date and time.
- 9) Remind the subject to notify the site in case of a SAE, and AESI.
- 10) For woman of childbearing potential: remind the subject to notify the site in case of pregnancy.
- 11) Complete the relevant source document information and CRF pages for this visit.

V03 (7 [+1] days after VAC1): Collection of Safety Information and Vaccination

- 1) Review the DC1 with the subject, including any AEs, SAE, AESIs, medications, or therapy that occurred since vaccination by Investigator or delegate. The subject will continue using the DC1 to collect safety information until V04.
- 2) Urine pregnancy test, if applicable.
- 3) Conduct a physical examination, including temperature.
- 4) Check contraindication for subsequent vaccinations (see [Section 5.2.7](#)).
- 5) Contact the IRT system for dose number assignment (see [Section 6.6](#)).

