6.4 Identity of Other Product

Imogam Rabies-HT Licensed HRIGs will be administered at D0 in all subjects from arms 1 to 3 included in the trial.

Form: Liquid/Solution in 2-mL vials

Route: IM injection in the anterolateral thigh

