12.2.3 Per-Protocol Analysis Set

The Per-Protocol Analysis Set (PPAS) is a subset of the FAS.

As D28 is the time point used for primary objective assessment, the PPAS will be defined at D28 (V05). The subjects presenting with at least one of the following relevant protocol deviations before D28 (ie, 14 days after the fourth vaccine injection) will be excluded from the PPAS:

- Subject did not meet all protocol-specified inclusion criteria or met at least one of the protocol-specified exclusion criteria
- Subject did not receive the first 4 doses of the vaccination schedule
- Subject received a vaccine other than the one that he / she was randomized to receive
- Preparation and / or administration of vaccine (including HRIG for groups 1 to 3) was not done as per-protocol for the first 4 vaccinations
- Subject did not receive the first 4 vaccine injections in the proper time window
 - Vac2 in [D03-D05]
 - Vac3 in [D07-D09]
 - Vac4 in [D13-D16]

- Subject did not provide the post-dose 4 serology sample at V05 in the proper time window [D25-D31] from D0
- Subject received a protocol-prohibited therapy/medication/vaccine (belonging to categories 2 and 3) before V05
- Subject's serology sample is missing or did not produce valid test results at both D0 and D28
- Seropositive subject at D0, ie, RVNA titer \geq LLOQ
- Subject developed a protocol-specified withdrawal criterion during the study but was not withdrawn
- Subject did not receive the correct amount of HRIG at D0

Adherence to the definition of the PPAS analysis set may also be decided during the blinded data review, ie, before breaking the code and locking the data base.

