3.3 Derived Endpoints: Calculation Methods

3.3.1 Safety

Terms used in the standard safety tables to describe the safety events are specified below.

- AE: Adverse event includes solicited reaction and unsolicited event (including non-serious and serious adverse events).
- Adverse Reaction (AR): Corresponds to AE related to the study vaccine (investigational product), unless otherwise specified.
- Immediate: Unsolicited systemic AE checked “Yes” in the field of “immediate (within 30 minutes from the vaccination)” by the Investigator in the electronic case report form (eCRF).
- Solicited reaction: Event pre-listed in the eCRF, and which occurred during the solicited period (up to 7 days after the day of each vaccination).
- Unsolicited AE: AE recorded in the eCRF as unsolicited systemic event or unsolicited injection site reaction.
- Unsolicited injection site reactions are to be considered as related to the study vaccine injection and therefore will be analyzed as ARs.

Note: HRIG being an additional study medication (non-investigational product), any AEs occurring at HRIG injection location will be reported as unsolicited systemic events in this study.

- Unsolicited AEs will be analyzed up to 28 days after any and each vaccination. Unsolicited AEs occurring before or after the defined period will not be presented in the summary for unsolicited AEs but will be presented in a separate listing. The exceptions are SAEs and AESIs which are unsolicited AEs collected during the whole study period (after the first vaccination to end of 6 months safety follow-up period).
- SAE: Unsolicited AE considered serious by the Investigator (reconciled with Global Pharmacovigilance database).
- AESI: Is one of scientific and medical concern specific to the Sponsor's product or program, for which ongoing monitoring and rapid communication by the Investigator to the Sponsor can be appropriate. The Medical Dictionary for Regulatory Activities (MedDRA) preferred terms (PT) defined in the protocol are:
 - Anaphylactic reaction (PT)
 - Encephalitis (PT)
 - Convulsion (PT)

3.3.1.1 **Solicited Reactions**

3.3.1.1.1 **Daily Intensity**

All daily records for solicited reactions will be derived into daily intensity according to the following classification: None, Grade 1, Grade 2, Grade 3, or Missing (Unknown).

For the derivation of daily intensity, the following sequential steps will be applied:

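### The stop rule in protocol Section 5.2.7.2 covers any immunoglobulin in the past 3 months and does not exempt the trial's own D0 HRIG, so as written it bars VAC2 to VAC5 in Groups 1 to 3

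*Protocol*

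**What the plan says.** Protocol Section 5.2.7.2 (Definitive Contraindications) is mandatory: if a listed condition is present, the Investigator stops vaccination. One item on the list is "Immunoglobulin, blood or blood-derived products received in the past 3 months or ongoing at the visit".

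Section 5.1.1 assigns immunoglobulin to three of the four arms: "All groups with the exception of Group 4 will additionally receive HRIG at D0". Section 6.4 repeats this: "Imogam Rabies-HT Licensed HRIGs will be administered at D0 in all subjects from arms 1 to 3 included in the trial". Section 5.1.1 also gives every subject vaccine at D0, D3, D7, D14 and D28.

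The contraindication list is consulted before later doses. The Table of Study Procedures has a row for "Definitive contraindications" ticked at V02 to V05. The step lists in Section 5.1.4 for V02, V03 and V04 include "Check contraindication for subsequent vaccinations", with a cross-reference to Section 5.2.7.

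The per-protocol criteria in Section 12.2.3 treat HRIG as required treatment. One ground for exclusion is "Subject did not receive the correct amount of HRIG at D0".

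**The concern.** The stop rule and the dosing schedule give opposite orders for the same subjects. A subject treated correctly at V01 in Groups 1 to 3 has received an immunoglobulin within the look-back period at every later vaccination visit. Section 5.2.7.2 then says stop, and the schedule says inject.

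The wording closely follows exclusion criterion 7 in Section 5.2.5, "Receipt of immune globulins, blood or blood-derived products in the past 3 months". That criterion works at enrollment because trial HRIG has not yet been given. Reused after D0 without an exception, it catches the trial's own treatment.

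At stake is the clarity of an operative rule. Staff have to supply an exception that the protocol does not state, and they have to do so in all three arms of the primary comparison.

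**Working it through.** There is no figure in the plan to reproduce. The check compares the texts and counts days and subjects.

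**1. Is study HRIG within the wording?** Yes. Section 6.4.1 gives its composition as human rabies immunoglobulins. The item covers any immunoglobulin and is not limited by source or purpose.

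**2. Has it been received before each check?** Yes. In the V01 steps of Section 5.1.4, HRIG is step 12, directly after VAC1 at step 11. Every later contraindication check therefore follows it.

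**3. Is each later visit inside the look-back period?** Taking 3 months as about 90 days:

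| Visit | Nominal days since HRIG | Latest day in the visit window |
|---|---|---|
| V02 (VAC2) | 3 | 3 |
| V03 (VAC3) | 7 | 7 + 1 = 8 |
| V04 (VAC4) | 14 | 14 + 1 = 15 |
| V05 (VAC5) | 28 | 28 + 3 = 31 |

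The longest in-window gap is 31 days, so the condition is met at all four visits. The V05 step list omits the check that the procedures table ticks for V05. This does not matter here, because the conflict already exists at V02.

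**4. Is there an exemption anywhere?** None was found in Section 5.2.7, 5.1.4, 6.4 or 6.9, or in the SAP. The item on other vaccines in the same list does exempt the study vaccine. That exemption cannot be stretched to HRIG, because SAP Section 3.3.1 classes HRIG as an additional study medication that is not an investigational product.

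**5. How far does the wording reach?** Group sizes are from protocol Table 5.1.
- Subjects: 318 + 106 + 106 = 530.
- Share of planned enrollment: 530 / 636 = 83.3%.
- Planned VAC2 to VAC5 injections in these groups: 530 × 4 = 2,120.
- Group 4 (106 subjects) receives no HRIG and is unaffected.
- With an exemption for study HRIG, 0 of 636 subjects would meet the item because of the trial regimen.

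**6. What is intended?** Section 12.2.3 requires both the first four vaccine doses and the correct amount of HRIG. Under the literal rule no subject in Groups 1 to 3 could satisfy both, and the primary comparison could not be made. The intended meaning must be immunoglobulin other than the study product.

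**The case against.** The strongest reply is that nobody would read the rule literally. The protocol orders HRIG and then four more vaccine doses for the same subjects, repeatedly and specifically, and a generic list item should give way to that. The lead-in speaks of a subject experiencing a condition, which suggests a new event rather than assigned treatment. The documents attribute incomplete or out-of-window vaccination to the SAE hold (71 subjects) and the COVID-19 stop (29 subjects), and neither sample-size revision mentions losses through this rule. The Operating Guidelines and site training may state the exception, but they are not available for review. On cost, Section 5.4 requires ethics committee approval even for administrative amendments. The planned vaccination period ended in Q3 2020, and the SAP version history dates the first database lock to 28 May 2021, so a change to these documents now would come too late for the subjects vaccinated.

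Most of this stands as an argument about practical effect: the intent is recoverable and no harm is documented. It does not supply the missing exemption. The item is defined by receipt within a look-back period, not by novelty, and HRIG is given after inclusion and randomization, so it falls within even an after-enrollment reading. That the rest of the protocol must override the item confirms that the item is wrong as worded.

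**Conclusion.** The point holds. Section 5.2.7.2 is wrong as written: it omits an exemption for study HRIG and so contradicts the vaccination schedule for Groups 1 to 3. Its literal reach is 530 of 636 planned subjects at each visit from V02 to V05. This rests on the planned group sizes, on visits held within their windows, and on 3 months being about 90 days.

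The consequence is limited. It is a drafting omission in an operative rule, not a flaw in the statistical design. No loss of subjects, per-protocol membership or power is projected, and alpha, the endpoint and the estimate are unchanged. It should be corrected because a mandatory vaccination stop rule ought to be right on its face.

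**What to change.** In the immunoglobulin item of Section 5.2.7.2, insert after the list of products the clause *other than the study HRIG administered at D0*. This parallels the exemption already given to the study vaccine in the same list.

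No matching note is needed in the per-protocol criteria (protocol Section 12.2.3, SAP Section 4.2.2). They exclude only therapy that the protocol prohibits, and HRIG that the protocol mandates is not prohibited.

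The cost is one clause and, under Section 5.4, ethics committee approval of the amendment that carries it. No data collection, procedure or analysis changes.
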